## **17.0 Process to Document Consent in Writing**

*17.1 Describe whether you will be following “SOP: Written Documentation of Consent (HRP-091).” If not, describe whether and how consent of the subject will be obtained including whether or not it will be documented in writing.*

Response: We will be following HRP-091.

## **18.0 Data and Specimen Banking\***

*18.1 The sponsor’s protocol may require banking data or specimens for future use and both storage and use will be determined by the sponsor. If additional data or specimens will be banked locally for future use, describe where the specimens will be stored, how long they will be stored, how the specimens will be accessed, and who will have access to the specimens.*

PROTOCOL TITLE: Open-label, single-blinded, observational, prospective, 36-month, longitudinal, controlled study to assess the efficacy of siponimod (Mayzent®) on microglia in patients with secondary progressive forms of multiple sclerosis

Response: Data will be kept on site for the duration of the study and archived thereafter for the requisite 7 years. Hard copies will be locked in a separate, secure filing room open only to project coordinators and clinical trial managers. Electronic data will be kept on a password- and dual firewall-protected server available only to MRI analysts, physicists, technical-, and clinical-support staff.

*18.2 List the data to be stored or associated with each specimen banked locally.*

Response: MRI data with superimposed region of interest (ROI) files will be saved on the server. CRFs, clinical data and informed consent will all be kept and archived in BNAC. Data will be centrally managed by BNAC on a secure network. The network is password protected and can be accessed only by personnel as directed by the BNAC Director. Clinical data is stored in BNAC in coded charts that do not contain names, only study identifiers. All CRFs, MRI data, informed consent and other study data will be kept and archived in BNAC. The data will be quality controlled by BNAC and Jacobs MS Center staff. Information related to data will be treated in strict confidence to the extent provided by law.

*18.3 Describe the procedures to release locally banked data or specimens, including: the process to request a release, approvals required for release, who can obtain data or specimens, and the data to be provided with specimens.*

Response: A password-protected database will be sent to the sponsor at his/her written request. No data will otherwise be shared with any organization or entity.

## Statistical Analysis Plan

**“Open-label, single-blinded, comparative, prospective, 36-month, longitudinal, controlled study to assess the efficacy of siponimod (Mayzent®) on microglia in patients with active secondary progressive forms of multiple sclerosis”**

**2023-09-15**

All statistical analyses were performed using SPSS version 28.0 (IBM, Armonk, NY, USA). The data distribution was determined using visual inspection of the histograms and Q-Q plots.

Categorical data was compared using chi-square test, parametric numerical data was compared using Student's t-test and non-parametric data using Mann Whitney U test. The comparisons between the groups were further adjusted for demographic and genetic differences using analysis of covariance (ANCOVA) and adjusted estimated means were shown as mean (standard error).

Due to the small sample size and non-parametric nature of the data, the correlations were performed using non-parametric Spearman's test. Pair-wise comparisons within the subjects were also performed. P-values lower than 0.05 were considered statistically significant. Due to the exploratory nature of the study, corrections for multiple comparisons were omitted. The data was additionally visualized using box and scatter plots.

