## 1.0 Study Summary

Study Title	Open-label, single-blinded, observational, prospective, 36-month, longitudinal, controlled study to assess the efficacy of siponimod (Mayzent®) on microglia in patients with active secondary progressive forms of multiple sclerosis
Study Design	Open label, single-blinded, observation, prospective, longitudinal BNAC MRI analysts are blinded to subject's medication treatment.
Primary Objective	The assessment of the effect of Mayzent over at least 24 months on the evolution of microglia pathology in patients with active secondary-progressive (SP) MS.
Secondary Objective(s)	(a) compare the effect of Mayzent to the control group of active SPMS patients treated with ocrelizumab (Ocrevus®), as measured by changes in microglial activation in the lesional and non-lesional normal appearing (NA) WM and GM, and in the peri-plaque area of chronic lesions in the brain; (b) the relationship between changes in microglial activation in the lesional and non-lesional normal appearing

PROTOCOL TITLE: Open-label, single-blinded, observational, prospective, 36-month, longitudinal, controlled study to assess the efficacy of siponimod (Mayzent®) on microglia in patients with secondary progressive forms of multiple sclerosis

	
(NA) WM and GM, and in the peri-plaque area of chronic lesions in the brain and clinical and behavioral outcomes.
 
(b) to validate the quantification approach and to use as a statistical control group (15 HCs) when looking at an increase in TSPO in a parametric map of the brain

Research Intervention(s)/ Investigational Agent(s)	MRI and PET scans, clinical visits, questionnaires, eye exam, blood sampling.
IND/IDE #	
Study Population	
Individuals with active Secondary Progressive Multiple Sclerosis (SPMS)
 
Activity is determined by MRI activity (contrast-enhancing lesions; new and unequivocally enlarging T2 lesions) and/or clinical relapses in the 24 months prior to the study baseline.
 
15-age-matched healthy controls (10 females and 5 males aged between 18-65 years)

Sample Size	60 MS patients; 15 healthy controls
Study Duration for individual participants	
2-3 years: MS Patients
 
Approximately 4 hours: healthy controls – 1 timepoint

Study Specific Abbreviations/ Definitions	

AEs	Adverse Events
BBB	Blood-brain-barrier
BICAMS	Brief International Cognitive Assessment for MS
BNAC	Buffalo Neuroimaging Analysis Center

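### Associations are tested by unadjusted Spearman only, although the same SAP adjusts group comparisons for demographics and genetics; adjusted coefficients should be reported beside the planned ones

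*Combined protocol and SAP*

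**What the plan says.** The SAP's opening text on statistical methods treats two kinds of analysis differently.

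- **Group comparisons.** After the t-test or Mann-Whitney test, these were "further adjusted for demographic and genetic differences using analysis of covariance (ANCOVA"). The covariates are not listed by name.
- **Correlations.** "Due to the small sample size and non-parametric nature of the data", "the correlations were performed using non-parametric Spearman's test". No partial, stratified or regression form is given here or anywhere else in the documents. The SAP does not say which variables are correlated, or whether the treatment arms are combined.

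The threshold is the same throughout: "P-values lower than 0.05 were considered statistically significant". Also, "Due to the exploratory nature of the study, corrections for multiple comparisons were omitted".

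The objective that needs an association analysis is the first secondary objective lettered (b) in section 1.0 of the Local Supplement: "the relationship between changes in microglial activation in the lesional and non-lesional normal appearing" white and grey matter, and "in the peri-plaque area of chronic lesions in the brain and clinical and behavioral outcomes".

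Three other places matter. Section 2.1 says treatment is chosen in routine care by the neurologist and the patient, so arms are not randomised. The abbreviation list defines high, mixed and low TSPO affinity classes, so genotype is recognised as a factor in binding. The SAP's PET analysis section divides regional uptake by cerebellar uptake.

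**The concern.** The reason given for Spearman concerns sample size and distribution. Ranking deals with outliers and skew, but not with a third variable that moves both quantities. The SAP recognises that demographic and genetic differences can distort a comparison between groups, yet leaves the associations exposed to them and gives no reason.

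The covariates do not all act in the same way:

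- **Age** may be related to both the PET measure and disability or cognition. It can then produce a correlation where there is none, or cancel one if it acts in opposite directions.
- **Treatment arm** can do the same, but only if the arms are pooled and differ on both variables.
- **TSPO genotype**, if it affects tracer binding alone, adds variation to one variable. That weakens a real correlation and does not create one.

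At stake is the interpretation of the secondary objective. A reported link between microglial change and outcome could be no more than a shared dependence on age or arm, and a real link could be missed.

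**Working it through.** The plan gives no power, effect size, SD or expected correlation, so there is no stated figure to reproduce. Everything below is illustration under stated assumptions.

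**Inputs from the documents.** Significance level 0.05 (SAP; two-sided assumed). Planned enrolment of 60 MS patients (section 1.0). MS enrolment and follow-up closed in revision 5, with no achieved number given, so n = 20, 30 and 60 are used as a range.

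**Assumed inputs.** All covariate effects, a 1:1 arm split and a 50% share for a two-level genotype.

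**Closed-form check**

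- Age correlated a with each variable, which are otherwise unrelated: induced r = a × a. For a = 0.4, r = 0.16; for a = 0.5, r = 0.25.
- Arms d SD apart on both variables, pooled 1:1: induced r = (d²/4)/(1 + d²/4). For d = 0.5, 0.0625/1.0625 = 0.06; for d = 0.8, 0.16/1.16 = 0.14.
- Rejection rate by Fisher z, with SE = √(1.06/(n − 3)). For r = 0.16: 13% at n = 30 and 22% at n = 60. For r = 0.25: 25% and 47%.
- Genotype shifting PET only by g SD, with carrier share p: attenuated r = r/√(1 + p(1 − p)g²). For r = 0.40, p = 0.5, g = 1: 0.40/√1.25 = 0.36.

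**Simulation.** There were 4,000 data sets per setting. Plain Spearman was compared with partial Spearman: ranks residualised on age rank, arm and genotype, with n − 2 − 3 degrees of freedom. The Monte Carlo standard error at 5% is √(0.05 × 0.95/4000) = 0.3 points.

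No true association, per cent significant at n = 20 / 30 / 60:

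| Assumed setting | Plain Spearman | Partial Spearman |
|---|---|---|
| No covariate effect | 4.8 / 5.2 / 5.6 | 4.8 / 5.2 / 5.6 |
| Age 0.3 with both | 6.4 / 7.4 / 10.1 | 5.5 / 5.0 / 4.8 |
| Age 0.5 with both | 17.0 / 24.0 / 45.9 | 6.0 / 5.1 / 4.8 |
| Arms 0.5 SD apart on both | 5.5 / 6.1 / 6.4 | 5.1 / 4.8 / 4.3 |
| Arms 0.8 SD apart on both | 8.6 / 11.0 / 17.6 | 4.7 / 4.9 / 5.1 |
| Genotype 1 SD, PET only | 5.4 / 5.4 / 5.2 | 5.4 / 5.2 / 5.5 |

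True correlation 0.40 given the covariates, per cent power at n = 20 / 30 / 60:

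| Assumed setting | Plain Spearman | Partial Spearman |
|---|---|---|
| No covariate effect | 37.2 / 54.8 / 86.2 | 32.5 / 49.8 / 84.2 |
| Genotype 0.5 SD, PET only | 35.6 / 52.3 / 83.2 | 32.4 / 49.4 / 83.7 |
| Genotype 1 SD, PET only | 29.8 / 42.8 / 75.4 | 31.7 / 48.8 / 83.1 |
| Age +0.5 and −0.5 | 5.5 / 6.2 / 6.7 | 27.5 / 45.4 / 79.8 |
| Arms +0.8 and −0.8 SD | 11.7 / 15.3 / 29.4 | 31.8 / 48.8 / 83.9 |

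The age-masking row follows from (0.5 × −0.5) + 0.75 × 0.40 = 0.05: almost nothing of the true 0.40 is left to detect. The simulated and closed-form results agree closely (for age at 0.5, 24% and 46% against 25% and 47%). The first row of the second table gives the price of adjusting when nothing is confounded: 4.7, 5.0 and 2.0 points of power.

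**The case against.** The other side has good arguments, and several of them stand.

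**Arm is not an inconsistency.** A reader might infer that the SAP already adjusts group comparisons for treatment arm and forgets it for correlations. It does not: arm is the factor being compared. Age and TSPO genotype are sensible readings of demographics and genetics, but neither is named.

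**Pooling is not stated.** A reader might also infer that the arms are combined and differ. The SAP says neither, so the arm effect is conditional on both. The link to the secondary objective is also an inference, though no other association method is offered for it.

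**Genotype is partly handled already.** The cerebellar ratio would largely remove an effect that scales all regions alike. A fixed additive offset drops out of within-subject change. Neither cancellation need be complete, and neither step removes age or arm effects.

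**The harm may be small.** With age at 0.3, or arms 0.5 SD apart, error rates barely leave the nominal level. The n = 60 figures use planned enrolment, and the SAP itself calls the sample small.

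**The study is exploratory and the analysis is written in the past tense.** This argues against replacing the planned test after the fact. It does not argue against showing an adjusted result too. Exploratory status is the SAP's reason for omitting multiplicity correction, and it did not stop the SAP from adjusting the group comparisons.

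**The wider protocol is not visible.** The Local Supplement's instructions say the sponsor protocol is uploaded separately. It could name covariates, but the SAP at hand does not.

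**Conclusion.** The point holds as a moderate, inexpensive improvement to a secondary analysis. As written, the plan leaves its only association method open to shared-covariate confounding.

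How much this matters cannot be known from the documents. Under the assumptions shown, the false-positive rate is about 6–10% with mild confounding. With age correlated 0.5 with both variables it is 17% at n = 20, 24% at n = 30 and 46% at n = 60. Masking can be severe if age acts in opposite directions on the two variables. Dilution by genotype is modest: a 1 SD shift takes power from 55% to 43% at n = 30 and from 86% to 75% at n = 60, before any relief from the cerebellar ratio or change scores.

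The documents do not support three stronger conclusions: that genotype alone can manufacture a correlation, that the correlations reported are in fact spurious, or that the planned Spearman test must be withdrawn. The first would need genotype to be linked to outcome or arm as well, which nothing in the documents suggests.

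**What to change.** Keep the planned Spearman coefficients and add to the SAP:

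1. State which PET measures and outcomes are correlated, whether as levels or changes, and whether the arms are pooled.
2. For each, report a partial Spearman correlation (rank residuals) adjusted for age and TSPO genotype, and for treatment arm when arms are pooled. Give 95% confidence intervals.
3. Show the unadjusted and within-arm coefficients in the same table.
4. Do not claim an association independent of these covariates unless the adjusted coefficient supports it.
5. Because the SAP postdates the closure of MS follow-up, label the adjusted coefficients as an added analysis.

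Limit the covariates to these three. Adding sex or others is hard to justify in a small sample.

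The cost is a few SAP sentences and a rerun on data already held. Age and arm take one degree of freedom each. Genotype takes one or two, depending on whether all three affinity classes are present, so the total is three to four. The power loss given above was calculated with three. Adjusting for arm also removes change in both variables that treatment itself produced, which may be part of what the objective asks about. That is why the unadjusted coefficient should stay visible.

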### **Revision History**

Revision #	Version Date	Summary of Changes	Consent Change?
1	24/06/2021	Change based on the new study protocol	Yes
2	28/02/22	Addition of Dent Institute as a recruitment and testing site	New MS consent for DENT; Yes to current MS consent form

PROTOCOL TITLE: Open-label, single-blinded, observational, prospective, 36-month, longitudinal, controlled study to assess the efficacy of siponimod (Mayzent®) on microglia in patients with secondary progressive forms of multiple sclerosis

3	07/04/2022	Inclusion of 15 healthy controls to undergo 1 PET scan and 1 MRI scan.	New HC consent form
4	11/9/2022	Including Great Lakes Medical Imaging as a PET scanning site	No
5	03/03/2023	Closing enrollment and follow-up of MS patients; Closure letter; continued enrollment of HCs	Yes - HC

PROTOCOL TITLE: Open-label, single-blinded, observational, prospective, 36-month, longitudinal, controlled study to assess the efficacy of siponimod (Mayzent®) on microglia in patients with secondary progressive forms of multiple sclerosis

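### For regional PET SUVR, the SAP defines no change measure and no model that uses every scan, so the arm difference in change over visits has no stated analysis

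*Combined protocol and SAP*

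**What the plan says.** The primary objective (Local Supplement, 1.0 Study Summary) is "The assessment of the effect of Mayzent over at least 24 months on the evolution of microglia pathology". Secondary objective (a) compares siponimod with ocrelizumab on changes in microglial activation in lesions, normal-appearing tissue and the peri-plaque area. Section 10.5 pays MS patients for five visits, and the lesion-activity part of the SAP gives the times as baseline, 6, 12, 24 and 36 months.

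The inferential plan is one short section of the SAP, dated 2023-09-15:

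- Between groups, unadjusted: "parametric numerical data was compared using Student's t-test and non-parametric data using Mann Whitney U test".
- Between groups, adjusted: "The comparisons between the groups were further adjusted for demographic and genetic differences using analysis of covariance (ANCOVA").
- Within patients: "Pair-wise comparisons within the subjects were also performed".
- Error control: "P-values lower than 0.05 were considered statistically significant", and "Due to the exploratory nature of the study, corrections for multiple comparisons were omitted".

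The SAP names no mixed model, repeated-measures ANOVA, GEE or arm-by-visit term. It does not say which visits are paired, at which visit the arms are compared, or what happens when a visit is missing. The PET analysis section ends with an SUVR per region, referenced to the cerebellum.

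The Revision History records, for revision 5 of 03/03/2023: "Closing enrollment and follow-up of MS patients; Closure letter; continued enrollment of HCs". The SAP is dated six months later and does not mention it.

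**The concern.** PET carries the microglial question, and that question is about change. For SUVR the plan leaves three gaps.

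1. **No change quantity.** Nothing defines a change in SUVR, and the baseline SUVR is not among the stated ANCOVA covariates.
2. **No arm difference in change.** A paired test within siponimod and another within ocrelizumab give two p-values. Neither they nor a comparison of them estimates the difference in change between arms, which secondary objective (a) needs.
3. **Pairs lost after closure.** A paired test keeps only patients with both scans. If patients entered over many months and follow-up then stopped for all, later pairs would be fewer and would come from earlier enrolees. The baseline and intermediate scans of the other patients would add nothing to that comparison.

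At stake are precision in a sample the SAP itself calls small, and whether the reported tests answer the stated objectives.

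**Working it through.** **No figure to reproduce.** The documents give no power calculation, effect size, SD, within-patient correlation, retention, achieved sample size or scans per visit. What follows is illustrative.

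**Dates.** From revision 1 (24/06/2021) to revision 5 (03/03/2023) is 617 days; 617 / 30.44 = 20.3 months. The documents do not say when the first MS patient started. If none started before revision 1, none reached month 24 by closure, and no model recovers that visit.

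**Which outcomes are affected.** The brain-volume section defines PBVC, PCVC and PTVC as percentage changes between scans. The lesion section identifies new and enlarging T2 lesions against the previous scan. A test between arms on any of these already compares change. SUVR has no such definition.

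**Precision: assumptions.** 30 patients per arm (half of the planned 60, a target now marked no longer applicable); unit SD; equal correlation rho between visits, 0.5 or 0.7; retention 100/90/60/25% at 0/6/12/24 months, with monotone loss. The 24-month column stands for a last visit that few reach. It is not a claim that anyone reached month 24.

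**Complete pairs only.** With n pairs per arm, the SE of the arm difference in change is √[2 × 2(1 − rho) / n].

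- Month 12, n = 0.60 × 30 = 18: √(4 × 0.5 / 18) = 0.333 for rho 0.5; √(4 × 0.3 / 18) = 0.258 for rho 0.7.
- Last visit, n = 0.25 × 30 = 7.5 (an expected count): √(4 × 0.5 / 7.5) = 0.516; √(4 × 0.3 / 7.5) = 0.400.

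**All scans.** Within each arm, sum the information over dropout patterns, I = Σ nₖ Eₖ′Vₖ⁻¹Eₖ, where Vₖ has 1 on the diagonal and rho elsewhere, and Eₖ selects the visits seen in pattern k. Then Var(change) = c′I⁻¹c, with c = −1 at baseline and +1 at the target visit. With separate baseline means the arms are independent, so the variance doubles for the arm difference.

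| Target visit | rho | SE, complete pairs | SE, all scans | Variance reduction |
|---|---|---|---|---|
| Month 12, 60% retained | 0.5 | 0.333 | 0.311 | 13% |
| Month 12, 60% retained | 0.7 | 0.258 | 0.244 | 11% |
| Last visit, 25% retained | 0.5 | 0.516 | 0.441 | 27% |
| Last visit, 25% retained | 0.7 | 0.400 | 0.346 | 25% |

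**Other patterns, within-arm change** (rho 0.5-0.85, or serial correlation 0.7-0.85 per 12 months). The figure is the all-scans variance divided by the complete-pairs variance.

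- Every patient has all visits, or two visits all paired: 1.00, so no gain.
- Per arm, 15 followed to month 12, 10 to month 6 and 5 at baseline only: 0.78-0.88 at month 12.
- Per arm, 10 each followed to months 24, 12 and 6: 0.69-0.78 at month 24. The baseline-to-24 pair uses 20 of 90 scans.
- Two visits, half the patients with baseline only: 0.88-0.96.

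**The case against.** The study calls itself exploratory, the sample is small, and the SAP describes the data as non-parametric. Simple tests are then a defensible choice, and a Gaussian mixed model brings assumptions of its own. This has weight: it rules out an elaborate model and calls for residual checks. It does not supply a contrast for secondary objective (a), and exploratory status is given in the SAP only as the reason for not correcting for multiplicity.

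Three stronger readings are tempting but not supported.

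- **That the SAP compares arms at single time points.** It does not state the visit or the variable. For the volume-change and new-lesion outcomes the tested quantity is already change. For SUVR the time point is simply unspecified.
- **That the 24-month objective has certainly been lost, or that late pairs are known to be few.** Revision 1 followed a new study protocol, so its date is not shown to be the first enrolment, and scans per visit are not reported.
- **That a mixed model would cut variance by about a third.** If the arms are assumed to share one baseline mean, the last-visit reductions rise to 33% (rho 0.5) and 29% (rho 0.7). Section 2.1 says treatment was decided in routine care by neurologist and patient, so equal baseline means cannot be taken for granted. Part of that larger gain also comes from baseline adjustment: against a baseline-adjusted ANCOVA of the same pairs, the shared-baseline model gains only 11% and 16%.

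The parent protocol is submitted separately and is not among these documents. If it defines the SUVR contrast, the SAP should cite it.

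**Conclusion.** The point holds for regional PET SUVR and should be acted on. The SAP names specific tests for a five-visit design. For SUVR those tests include no defined change, no stated baseline adjustment and no estimate of the arm difference in change. This part rests on the text alone and I hold it with high confidence.

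The cost in precision is conditional. It is zero for the within-arm change if all pairs are complete. Under the assumptions above, the variance of the arm difference in change would fall by about 11-13% at a month-12 visit with 60% retained and by 25-27% at a last visit with 25% retained. Achieved numbers, retention and correlation are not given, so these are illustrations and not estimates for this trial. They also take the loss of visits to be unrelated to the unseen SUVR values.

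**What to change.** For each regional SUVR, make the main analysis of the MS arms a linear mixed model on all available scans:

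- Fixed effects: visit, arm, arm-by-visit, age, sex and TSPO genotype.
- Baseline SUVR enters either as one of the responses or as a covariate for post-baseline visits, not both. State which, since with non-randomised arms the two choices need not answer the same question.
- A simple covariance such as compound symmetry. Unstructured over five visits has 5 × 6 / 2 = 15 parameters, too many for a small sample.
- Kenward-Roger or Satterthwaite degrees of freedom; check residuals and transform SUVR if skewed.

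Report scans per arm and visit. From the model, report the siponimod change and the arm difference in change at the latest visit with adequate scans, and say plainly if that is earlier than month 24. Keep pair-wise tests as descriptive. If only two visits exist, use ANCOVA of the follow-up SUVR with baseline SUVR added to the covariates. The change-based MRI outcomes do not need this change.

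The cost is SAP text and a rerun in the same software, with no new data. If SUVR results have already been seen, label the model as added afterwards. The downside is reliance on missing-at-random and on a working covariance that a small sample can check only weakly.
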